7.2.2 Severity

The severity of an AE is classified according to the following categories:

- Mild
- Moderate
- Severe

7.2.3 Causal relationship

The assessment of the causal relationship between an AE and the device or procedure is a clinical decision based on all available information at the time of the completion of the AE case report form. The assessment is based on the question whether there was a "reasonable causal relationship" to the procedure and/or device.

Possible responses to causal relationship are "related", "possibly related", or "not related".

- An assessment of "not related" would include (1) the existence of a clear alternative explanation (e.g., the subject develops a local infection from an unrelated laceration) or (2) non-plausibility (e.g., the subject is struck by an automobile when there is no indication that the device caused disorientation that may have caused the event).
- An assessment of "possibly related" indicates that there is a reasonable suspicion that the AE is associated with the procedure and/or device, but not definitively so.
- An assessment of "related" indicates that the AE is very likely associated with the procedure and/or device.

Important factors to be considered in assessing the relationship of the AE to the device or procedure include (1) the temporal sequence from the procedure—the event should occur after the procedure is initiated, (2) underlying, concomitant, intercurrent diseases—each event should be evaluated in the context of the natural history and course of the procedure and any other medical conditions the subject may have, and (3) concomitant medications or procedures—any drugs the subject is taking or the additional procedures the subject receives should be examined to determine whether any of them may be suspected to cause the event in question.

7.2.4 Anticipated

A list of anticipated adverse events is in Section 3.6.1. For this study, the applicable reference documents are this protocol and the Clinical Evaluation Report (G150265, Attachment H, pages 337-382). Classification of AEs as anticipated and unanticipated will be determined by the Investigator using the reference documents.

7.3 Assessments and documentation of adverse events

The Investigator must collect all AEs for each subject from the time of enrollment through the end of subject study participation, whether or not deemed related to the investigational device or procedure. A hospitalization or surgical procedure that was scheduled prior to subject enrollment should not be deemed an adverse event. All AE data will be recorded on the AE case report form. The Investigator must make an assessment and document it on the AE case report form. The Independent Medical Monitor will adjudicate all reported adverse events.

All AEs will be followed through resolution or until the AE is not expected to change. The subject will be referred to his or her primary care physician for any ongoing medical issues continuing beyond the completion of the study.

7.4 Reporting of serious adverse events and near incidents

The definition of SAE is provided in Section 7.1. These include device deficiencies that may have led to a SAE if a) suitable action had not been taken or b) intervention had not been made or c) if circumstances had been less fortunate.

Notification to sponsor: All serious adverse events (whether or not considered device-related) must be reported immediately (within 24 hours) to:

[name] **Clinical Operations** [contact] [contact] If e-mail receipt is not confirmed, please call to provide notification.

Notification of the IRB: Notification of the IRB about all relevant events will be performed by the Investigator according to all applicable requirements.

7.5 **Device Deficiencies**

The Investigator must document all device failures, malfunctions, and use errors, including the assessment whether the event is considered a near incident (ADE) using the Device Deficiency case report form. The case report form must be faxed or emailed to the Sponsor within 24 hours of Investigator knowledge of the event. If a device malfunctions, the Investigator must contact the Sponsor to determine if the device should be returned.

7.6 **Study Termination**

If new information is discovered during the study that indicates that the device or intervention provides an unreasonable risk to subjects, study enrollment will be suspended or discontinued. Enrollment will only be resumed once the risk has been appropriately mitigated and authorization to resume is obtained from FDA and the reviewing IRB. Regardless of ability to resume the study, all treated subjects will be followed as required by the protocol (6 weeks post-intervention).

The study or any clinical study site may also be halted or terminated early by the Sponsor for business reasons.

8.0 Data Collection, Reporting and Quality Assurance

8.1 **Case Report Forms**

Case report forms will be used to record demographic, intervention, and follow-up data, as well as any protocol deviations, adverse events, or device malfunctions that may occur during the study period.

8.2 **Protocol Deviations**

A Protocol Deviation Form must be completed for each study protocol deviation (e.g., failure to obtain informed consent, enrolling a subject who does not meet inclusion/exclusion criteria², not performing

PEARLE Study Page 29 of 36

² There may be times when the pre-treatment EBL is re-estimated after Device use. If the re-estimation of the pre-treatment EBL is greater than the maximum EBL allowed for study entry by < 20% (i.e. the re-estimate was < 1800 ml), then the site is not required to report a protocol deviation to the EBL

required testing, missed follow-up window, etc.). The Investigator must notify the Sponsor and the reviewing IRB of any deviation from the investigational plan that was done to protect the life or physical well-being of a subject (medical emergencies). Such notice should be given within 24 hours after the emergency occurred.

8.3 Efforts to Minimize Data Loss

If a subject fails to comply with the follow up evaluations, the study site must attempt to contact the subject at least three times, including once as a registered letter. In order to minimize loss to follow-up, during the hospitalization, the study coordinator will request that the subject provide names and contact information of two individuals that have a close relationship with the subject. The contacts will be utilized in the event that the subject relocates or cannot be reached by mail or telephone. This information will be treated as confidential and for use by the investigative site only.

8.4 Data Confidentiality

All information and data sent to the Sponsor, Contract Research Organizations, or their designated agents concerning subjects or their participation in this study will be considered confidential and identifying information should be redacted. All data used in the analysis and reporting of this evaluation will be used in a manner without identifiable reference to the subject. The Principal Investigator consents to visits by the staff of the Sponsor and its authorized representatives and the U.S. Food and Drug Administration or any other local governmental body to review the study subjects' medical records including any test or laboratory data.

All information concerning the device, such as patent applications, formulas, manufacturing processes, scientific data, specific study designs, protocols, and formulation information supplied by the Sponsor and not previously published is considered confidential and will remain the sole property of the Sponsor. The Principal Investigator agrees to use this information only in accomplishing the purposes of this study and will not use it for other purposes without the Sponsor's written consent.

8.5 Quality Assurance of the Data

Subject case report forms will be reviewed against source documentation for completeness and accuracy. If any discrepancies are noted, they will be resolved with the Investigator and/or designee. If the data are incomplete, attempts will be made to obtain the missing data.

8.6 Monitoring Procedures

The Alydia Health Vice President of Clinical Operations will have responsibility over the clinical study. Monitors, the Independent Medical Monitor, and associated personnel will be recorded in the Trial Master File.

The Sponsor is responsible for monitoring the study data to verify that the subject rights and well-being are protected in accordance with applicable regulations, GCP, and Sponsor/CRO procedures. The Sponsor, or Sponsor designee, will perform clinical monitoring, including review of case report forms with verification to the source documentation. Both remote and on-site monitoring may be conducted in this study. The Investigator will allow direct access to all relevant subject files for the purpose of verifying entries made in the case report form and assist with the monitor's activities as required. Adequate time, office accommodations, and resources (e.g., copy machine, phone, and/or internet access) for monitoring visits should be made available to the monitor at clinical sites.

PEARLE Study CIP-01 v2.6

eligibility criteria. If the re-estimated pre-treatment EBL is >1800 ml, then it must be reported as a protocol deviation.

Monitors will contact the site prior to the start of the study to review with the site staff the protocol, study requirements, and their responsibilities to satisfy regulatory, ethical, and Sponsor's requirements.

The Sponsor/designee will periodically monitor the site activity to verify:

- Data are authentic, accurate and complete.
- Safety and rights of subjects are being protected.
- Study is conducted in accordance with the currently approved protocol (including study treatment being used in accordance with the protocol).
- Any other study agreements, GCP, and all applicable regulatory requirements are met.

The Investigator and the head of the medical institution (where applicable) agree to allow the monitor direct access to all relevant documents.

8.7 Publication Policy

The Principal Investigator may not publish information obtained during this study prior to obtaining the review and approval of the Sponsor, which shall be in writing. The Sponsor reserves the right to assert its proprietary interests regarding any confidential, technical or proprietary information that the Sponsor may have furnished the Principal Investigator in order to facilitate clinical studies under this agreement.

9.0 Statistical Analysis Plan

9.1 Introduction

This is a prospective, single-arm, literature-controlled, multi-center trial designed to assess the safety and effectiveness of the Jada System when treating primary PPH. The study is designed to demonstrate that Jada provides safe and effective control or reduction of primary PPH. Safety will be evaluated by analyzing all adverse events for device relatedness, seriousness, severity, and whether or not they were anticipated.

Up to 20 study sites will enroll a total of up to 107 subjects in the study to ensure that 96 subjects are available for the analysis of the primary effectiveness endpoint. Qualified sites will be located in the U.S. and potentially O.U.S. as well. Sites are expected to enroll a minimum of 5 subjects. Site enrollment will be capped at 30% of the total expected enrollment, such that no site will enroll more than 32 subjects. Also, no more than 50% of the study data will come from O.U.S. sites.

9.2 Study Endpoint Analysis

Reported Adverse Events

Adverse events will be categorized as:

- serious or non-serious,
- severe, moderate or mild,
- device-related, possibly device-related or non-device-related,
- anticipated or unanticipated.

The frequency of each event will be summarized according to the above categories. Since some subjects may report the same event several times (e.g., headache), the first occurrence of the worst reported case of the event will be used for the purpose of analysis.

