4.2.2 Primary Safety Endpoint

Safety: Incidence, severity and seriousness of device-related Adverse Events.

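### Section 9.2 keeps one 'worst' record per subject for a repeated adverse event without defining worst, so a device-related or serious occurrence can be lost from the primary safety endpoint

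*Combined protocol and SAP*

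**What the plan says.** The primary safety endpoint (section 4.2.2) is "Incidence, severity and seriousness of device-related Adverse Events". Section 9.1 adds a general statement: "Safety will be evaluated by analyzing all adverse events for device relatedness, seriousness, severity, and whether or not they were anticipated".

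Section 9.2 lists four ways of categorising each event: serious or not; mild, moderate or severe; "device-related, possibly device-related or non-device-related"; and anticipated or not. It continues: "The frequency of each event will be summarized according to the above categories". For a woman who reports the same event more than once, with headache as the example, "the first occurrence of the worst reported case of the event will be used for the purpose of analysis".

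Sections 7.2.1 to 7.2.4 have the investigator assess these attributes separately: seriousness against the criteria in 7.1, severity on a three-level scale, causality as a clinical judgement, and anticipated status against reference documents. On collection, section 7.3 is comprehensive: "The Investigator must collect all AEs for each subject from the time of enrollment through the end of subject study participation", whatever the relation to the device. Safety is analysed in the Safety/ITT Cohort (section 9.6).

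**The concern.** A one-record rule is harmless when all attributes rank the occurrences in the same order. Here they need not. The most severe episode of cramping may be the one with a clear non-device cause. A moderate infection that leads to readmission is serious, while a severe one that does not may not be.

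The primary safety endpoint is defined by one attribute (device-related) and described by two others (severity and seriousness). If one record is selected on a single attribute before the device-related events are picked out, a woman who had a device-related event can be tabulated as not having had one. With no control arm and no safety threshold, the safety conclusion rests on these descriptive tables. An undefined selection rule also leaves the choice open until after the data have been seen.

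**Working it through.** **1. The plan's own safety figure.** Section 5.4.1 states a 95% chance of seeing at least one event among 96 treated women when the incidence is at least 3.1%. Check: 1 − (1 − 0.031)^96 = 0.951. Inversely, 1 − 0.05^(1/96) = 3.07%, which rounds to 3.1%. The figure reproduces. It assumes that every woman with the event is tabulated as having it.

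**2. What each reading of *worst* does.** Take a hypothetical woman with two occurrences of one event term:

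- A: mild, device-related, serious
- B: severe, not related, non-serious

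| Reading | Record kept | What is lost |
|---|---|---|
| Most severe, chosen across all occurrences | B | The device-related and the serious classification; she leaves the primary safety count for this term |
| Most related | A | The severe grade in the all-event table |
| Most serious | A | The severe grade in the all-event table |
| Device-related events first, then most severe | A | Nothing from the primary endpoint |
| Worst level on each attribute separately | no single record | Nothing |

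Two further checks bear on the remedy:

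- Restricting to device-related events first is not enough. Suppose both occurrences are related, C severe and non-serious, D moderate and serious. Choosing the more severe keeps C and loses the seriousness.
- Taking each attribute's worst level across all occurrences is not enough for the primary endpoint. In the A/B example it would pair B's severe grade with A's relatedness and overstate the severity of the device-related event. Both steps are needed: restrict first, then work attribute by attribute.

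**3. Size per woman.** The denominator is the Safety/ITT Cohort, whose final size is not fixed. The plan names 96 (evaluable target) and 107 (maximum enrolment). One woman lost from a count lowers the rate by 1/96 = 1.04 or 1/107 = 0.93 percentage points. The rate of any device-related event falls only if she has no other device-related event in the table.

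**4. Sensitivity, on an assumption.** The documents give no rate of discordant repeats. Suppose a share q of women with a given device-related event also has a more severe, unrelated occurrence of the same event, and the first reading in the table applies. A true incidence of 3.1% is then tabulated as 3.1% × (1 − q), and the chance of tabulating at least one case among 96 is 1 − (1 − 0.031(1 − q))^96:

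| q (assumed) | Tabulated incidence | Chance of at least one |
|---|---|---|
| 0 | 3.10% | 95.1% |
| 5% | 2.95% | 94.3% |
| 10% | 2.79% | 93.4% |
| 20% | 2.48% | 91.0% |
| 50% | 1.55% | 77.7% |

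Under the rule proposed below, q has no effect and the first row applies throughout.

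**The case against.** The strongest reply is that section 9.2 never equates *worst* with most severe. The sentence just before it promises a summary by each category, which fits a worst case taken within each table. The endpoint is itself confined to device-related events, so a programmer might well filter on relatedness first. Under either approach the A/B loss disappears. This stands: the loss is conditional. A reader might infer that the plan does discard device-related events whenever a more severe episode follows, and that the safety counts can only be biased downward. The documents do not support that. The downward direction holds for counts of device-related or serious events under the severity reading with selection across all occurrences. Even then, severity is not simply biased low, because losing milder device-related records can raise the severe share among those that remain.

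The loss also needs the same woman to have repeats of the same event with discordant attributes. Section 7.1.7 sets relatedness broadly, covering any event whose link to the device cannot be excluded, and the Independent Medical Monitor adjudicates all reported events. The feasibility study reported no device-related event in ten women (section 5.6). Discordant repeats may therefore be few, though the documents do not show how few.

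Finally, counting a woman once per event is a proper way to report subject-level incidence, all events are collected, and serious ones reach the sponsor within 24 hours. All of this is true, but none of it governs how repeats enter the endpoint tables. Complete collection does not correct a tabulation rule that discards a record, and the general statement in section 9.1 does not say how repeats are resolved.

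**Conclusion.** The point holds in conditional form. The plan reduces repeated events to one record, leaves *worst* undefined across four attributes that can disagree, and does not fix the order of selection and restriction to device-related events. Every single-record reading can lose a classification somewhere. The severity reading, applied across all occurrences, can remove device-related or serious occurrences from the primary safety endpoint.

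The amount of any understatement cannot be estimated from the documents. The supportable statement is about one percentage point per woman lost, with the sensitivity table as an illustration that rests on an assumed q. Study success (sections 4.3 and 9.4) depends only on the effectiveness confidence interval, so no formal decision is affected. The change should be made because the counts belong to a primary endpoint and a clearly better rule is nearly free.

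**What to change.** Replace the last sentence of the adverse event paragraph in section 9.2 with a rule such as:

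> Each subject is counted once per event term, separately on each attribute: device-related if any occurrence is related or possibly related; serious if any occurrence is serious; unanticipated if any occurrence is unanticipated; and at her maximum severity. For the primary safety endpoint, occurrences are first restricted to those that are device-related; severity is then the maximum, and seriousness is present if any is serious, among those occurrences. Numbers of events are shown beside numbers of subjects.

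Grouping related with possibly related follows the definition of a device-related event in section 7.1.7; the two levels can still be shown separately.

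The cost is a short SAP edit and slightly more table programming, with no new data. The downside for the sponsor is that the reported device-related rate may be less favourable. The edit should be made before the safety data are tabulated.

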9.3 Primary Effectiveness Endpoint – Treatment Success

Control of postpartum hemorrhage, defined as the avoidance of non-surgical, second line or surgical intervention to control uterine hemorrhage after the use of the Jada System per the Instructions for Use.

Non-surgical, second line procedures include uterine balloon therapy, uterine packing, or uterine artery embolization. Surgical intervention includes procedures such as uterine arterial ligation, uterine compression sutures or hysterectomy.

Note: Continuation of the administration of uterotonics concomitant with and post Jada use is standard of care as long as such use does not exceed the maximum dose of the drug and does not constitute failure of the primary effectiveness endpoint.

9.4 Study Success

A thorough review of all known publications reporting on the use of the Bakri Balloon and other balloon tamponade methodologies to treat PPH was conducted. A meta-analysis methodology was used to aggregate the studies and provide a numerical estimate of the overall Literature Treatment Success Rate. Based on a random effects model, the estimated pooled proportion of subjects who reached hemostasis (i.e., control of uterine hemorrhaging) following Bakri Balloon treatments was 82.0% (95% CI: 73.4% to 89.2%). See the Clinical Evaluation Report (G150265, Attachment H, pages 337-382).

The primary effectiveness objective of this Pivotal Study is to show that the observed Study Treatment Success Rate is not worse that the rate reported in the literature. The study is considered a success when the lower bound of the two-sided Exact Clopper-Pearson mid-p 95% Confidence Interval for the Study Treatment Success is greater than or equal to 73.4%.

9.5 Secondary Endpoints

- 1. Time to control hemorrhage, defined as the time from turning on the vacuum source until the time the *first* of any of the following occurs:
 - there is no blood being collected in the tubing or canister, or
 - the blood loss is observed as leveled off in the canister, or
 - blood loss at a rate of < 500 ml in 24 hours.
- 2. Rate of surgical intervention required to control PPH after Jada use.
- 3. Rate of non-surgical intervention required to control PPH after Jada use.
- 4. Assessment of device usability as reported by the clinician using a dedicated data collection form.
- 5. Rate of blood product transfusion required after Jada use, and number of transfusion units when administered.

The secondary endpoints will be summarized, and confidence intervals will be provided to support interpretation of the results. No specific hypothesis tests will be performed for the secondary endpoints.

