5.4 Study Population

5.4.1 Number of Subjects and Sample Size Calculation

Up to 107 subjects will be enrolled in the study to ensure that 96 subjects are available for the analysis of the primary effectiveness endpoint. Sites are expected to enroll a minimum of 5 subjects. Site enrollment will be capped at 30% of the total expected enrollment, such that no site will enroll more than 32 subjects.

The study is powered to show that the Treatment Success Rate among the Jada subjects is not inferior to the Treatment Success Rate derived from a meta-analysis performed using all known publications reporting on the use of the Bakri Balloon (and equivalents) to treat PPH.

Based on a random effects model used in the meta-analysis, the estimated pooled proportion of subjects who reached hemostasis (i.e., control of uterine hemorrhaging) following Bakri Balloon treatments was 82.0% (95% CI: 73.4% to 89.2%). See the Clinical Evaluation Report (G150265, Attachment H, pages 337-382).

Non-inferiority will be achieved when the lower bound of the Exact Clopper-Pearson mid-p 95% Confidence Interval for the Study Treatment Success Rate is greater than or equal to the lower bound of the 95% Confidence Interval of the Treatment Success Rate derived in the meta-analysis, or 73.4%. That is:

Statistical Hypothesis: $H_0: \pi_{Jada} \le \pi_{Literature \ CI \ LB} \ vs \ H_1: \pi_{Jada} > \pi_{Literature \ CI \ LB}$

where π_{Jada} is the Treatment Success Rate for Jada treated subjects and $\pi_{Literature\ CI\ LB}$ is the lower bound of the 95% Confidence Interval for the Treatment Success Rate derived from the meta-analysis of the Bakri

Balloon Literature.

Statistical Methodology: Confidence Interval for π_{Jada}

Expected π_{Jada} : 0.82

Half-width of 95% CI: 0.086

Confidence Level: Two-sided 95%

Minimum Sample Size: n = 96 evaluable subjects

Statistical Power: 0.806 that the lower bound will be greater than or equal to 0.734

With 96 evaluable subjects, there is an 80.6% probability that the lower bound of the observed Exact Clopper-Pearson mid-p two-sided 95% confidence interval will be expected to be greater than 0.734 when the Jada Treatment Success is expected to be 82%. (Calculated using SAS v9.4 PROC POWER.)

For safety, with 96 subjects treated with Jada, there is a 95% chance of observing at least one adverse event when the underlying incidence of the event is at least 3.1%.

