6.6 Post-procedure Follow-up

After removal of Jada and before subject discharge from the hospital, additional data collection is required. Information about the following will be collected on case reports forms:

- Physical Examination, including limited Pelvic Examination
- If done, CBC and coagulation panel results
- Clinician Assessment of Device Usability
- Assessment of any adverse events that occur from the beginning of device use to discharge

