9.8 Statistical Methods

Categorical data will be summarized using frequency tables, presenting the subject counts and relative percentages. McNemar's chi-square may be used to assess within-subject changes in a bivariate response variable.

Continuous variables will be summarized by the mean, standard deviation, median, minimum and maximum. Within-subject changes (Change-from-Baseline) will be analyzed parametrically using the Paired t-test if the differences are normally distributed, or non-parametrically using the Sign-Rank Test if the differences are not normally distributed.

The SAS system or equivalent statistical package will be used to perform all analyses. Exact confidence intervals will be generated for estimates of proportions. Asymptotic confidence intervals will be generated for estimates of means. The p-values of all tests will be reported without any correction for the multiplicity of tests performed.

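### The plan makes no provision for repeat usability ratings by one clinician; if they occur and are positively correlated, the usability confidence intervals will be too narrow

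*Combined protocol and SAP*

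**What the plan says.** Section 9.5 (and 4.2.3, in the same terms) lists as a secondary endpoint "Assessment of device usability as reported by the clinician using a dedicated data collection form". The respondent is therefore the clinician, not the woman treated.

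The timing is per procedure. Section 6.6 states "After removal of Jada and before subject discharge from the hospital, additional data collection is required", and the items collected then include "Clinician Assessment of Device Usability". Table 2 in section 6.8 places the usability assessment in the column running from the Jada procedure to discharge. This amounts to about one form per treated woman.

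On analysis, section 9.5 says "The secondary endpoints will be summarized, and confidence intervals will be provided to support interpretation of the results", followed by "No specific hypothesis tests will be performed for the secondary endpoints". The general methods in section 9.8 supply the only interval types: "Exact confidence intervals will be generated for estimates of proportions", and asymptotic intervals for means. Neither section mentions a clinician cluster, a random effect, a robust variance or a rule for repeat raters. Section 9.10 examines site differences, but only for Treatment Success.

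On numbers, section 5.4.1 plans up to 107 women to secure 96 evaluable, adds "Sites are expected to enroll a minimum of 5 subjects", and caps any site at 32. Section 5.2 allows 5 to 20 sites. Section 5.3 requires investigators to be trained and approved before using the device, but does not say how many there will be at each site.

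**The concern.** Two ratings by the same clinician share that person's opinion, skill and accumulated experience with the device. They therefore tend to resemble each other more than ratings by two different clinicians. A standard exact or asymptotic interval computed over all forms ignores this and counts each form as a full unit of new information.

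If clinicians rate more than once, the interval would overstate how precisely usability is known, and a few frequent users could carry much of the estimate. Because section 9.5 plans no test for secondary endpoints, the interval is the only inferential output for usability, and the plan offers it as the aid to interpretation. At stake is the stated precision of one descriptive endpoint, not the trial's conclusion.

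**Working it through.** The documents state no precision, width or sample size for usability, so there is no figure of the plan's own to reproduce. The check therefore asks what repeat rating would do to the interval the plan names.

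**Inputs from the documents**
- Forms: about one per treated woman, so 96 to 107 (5.4.1, 6.6).
- Sites: 5 to 20 (5.2), with an expected minimum of 5 and a cap of 32 women per site (5.4.1).
- Interval: exact for a proportion (9.8). Section 9.5 gives no level for the secondary intervals; 95% is assumed.

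**Inputs assumed, because the documents give none**
- Usability reduced to a favourable/unfavourable proportion with a true rate of 80% or 90%.
- Forms per clinician, m: 1, 2, 3, 5 or 8, equal across clinicians.
- Within-clinician correlation, ρ: 0.05, 0.2 or 0.5.

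**Step 1. Is repeat rating plausible?** Average forms per site run from 96/20 = 4.8 to 107/5 = 21.4. Only trained, approved investigators use the device. At the upper end, a site would need about 21 different users to avoid any repeat. At the lower end, a handful of investigators could rate once each. Some repeats are likely, but the documents do not establish them.

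**Step 2. Design effect.** DE = 1 + (m − 1)ρ. The interval should be √DE times as wide, and the effective number of forms is 96/DE.
- m = 1, any ρ: DE = 1, no change.
- m = 2, ρ = 0.2: DE = 1.2, width × 1.10, effective forms 80.
- m = 3, ρ = 0.2: DE = 1.4, width × 1.18, effective forms 69.
- m = 3, ρ = 0.5: DE = 2.0, width × 1.41, effective forms 48.
- m = 5, ρ = 0.5: DE = 3.0, width × 1.73, effective forms 32.

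For scale, at 80% favourable and 96 forms the normal-approximation half-width is 1.96 × √(0.8 × 0.2/96) = 8.0 percentage points. At m = 3, ρ = 0.5 it should be 8.0 × 1.41 = 11.3 points.

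**Step 3. Actual coverage of the exact 95% interval.** The number of favourable forms per clinician is taken as beta-binomial with mean equal to the true rate and correlation ρ. There are 96, 48, 32, 19 or 12 clinicians for m = 1, 2, 3, 5 or 8 (95 forms when m = 5). Coverage is the probability that the Clopper-Pearson interval over all forms contains the true rate.

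| True rate | ρ | m = 1 | m = 2 | m = 3 | m = 5 | m = 8 |
|---|---|---|---|---|---|---|
| 80% | 0.05 | 96.0% | 95.5% | 95.0% | 93.9% | 92.2% |
| 80% | 0.2 | 96.0% | 93.9% | 91.7% | 87.3% | 81.2% |
| 80% | 0.5 | 96.0% | 90.5% | 85.1% | 75.9% | 65.6% |
| 90% | 0.05 | 97.5% | 97.2% | 96.8% | 96.0% | 94.7% |
| 90% | 0.2 | 97.5% | 96.0% | 94.2% | 90.6% | 85.2% |
| 90% | 0.5 | 97.5% | 93.2% | 88.5% | 79.7% | 68.6% |

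The m = 1 column exceeds 95% because the exact interval is conservative. That margin absorbs most of the effect at ρ = 0.05. The simple approximation 2Φ(1.96/√DE) − 1 agrees in direction and size; for m = 3, ρ = 0.5 it gives 83.4%.

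**The case against.** The strongest reply is that the error is conditional on facts the documents do not contain. They do not give the number of clinicians, do not say that any clinician rates twice, and do not show the form's items or scale. A site with about five women and several trained investigators might yield one or two forms each. No interval is defined for usability itself; independence is inferred from general sentences in 9.8. Usability may be reported mainly as item-by-item counts. All of this stands, and it is why the point is worded as a condition.

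A reader might infer that the plan states every form is independent, or that the intervals are certainly too narrow. The text supports neither. A reader might also infer that the effective sample is closer to the number of clinicians than to the number of forms. That is not generally so: at m = 3 and ρ = 0.2 the effective number is 69, nearer to 96 forms than to 32 clinicians. It holds only with higher correlation or heavier repetition.

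It can also be said that usability per use is as reasonable a target as usability per clinician, in which case frequent users properly carry more weight. That is fair, and it argues against replacing the all-forms estimate with a first-use summary. It does not rescue the interval: even for the per-use estimate, correlated ratings from the same people carry less information than independent ones.

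Finally, no test, threshold or success rule uses this interval. That stands and limits the importance of the point.

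**Conclusion.** The concern holds in conditional form. The plan collects clinician ratings about once per woman, promises intervals, and names only methods that in standard form assume independent observations. It neither defines the usability summary nor says how repeat ratings by one clinician will be handled. If repeats occur with positive correlation, the intervals will be too narrow.

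The size cannot be fixed from the documents. Over the assumed range it runs from negligible (ρ = 0.05, or few repeats) to serious (coverage near 66% at eight forms per clinician and ρ = 0.5). The result rests on a binary summary, equal numbers of forms per clinician and the assumed values of m and ρ.

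This is a low-priority improvement to a descriptive secondary endpoint. Study Success rests on the primary effectiveness endpoint in the Safety/ITT Cohort (9.4, 9.6) and is unaffected.

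**What to change.** In sections 9.5 and 9.8:
- Define the usability summary (which items, and whether a proportion or a mean).
- Record a coded rater identifier on the usability form, and report the number of clinicians and the distribution of forms per clinician.
- Compute usability intervals with the clinician as the cluster, by a clinician-level bootstrap or a cluster-robust variance with a small-sample correction.

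A summary of each clinician's first use is optional. It shows usability without a learning effect, but it answers a different question and at three forms per clinician discards two thirds of the data.

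The cost is a few sentences of SAP text, minor programming and possibly one form field, since the documents do not show whether the form already identifies the rater. The field is best secured before data are collected, because the rater may be hard to reconstruct later. The downside is somewhat wider usability intervals.
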